9.4 Power and Sample Size

With the planned sample size is 15, a two-sided 95% confidence interval for a single proportion will extend 25.3% from the observed proportion for an expected proportion of 50%; if the proportion is low or high, such as 10% or 90%, a two-sided 95% confidence interval will extend 15.2% from the observed proportion. If the outcome is continuous, with an n of 15, power of 80% and a 2-sided alpha of 0.05, the confidence interval around the estimate would have a width of approximately 1.02 standard deviations.

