6.0 Intervention Plan

The study aims to initially recruit a single cohort of 15 patients. This is a virtual group interventional design in which investigators distribute the electronic assessment battery, perform the intervention, assess mid-way through, and reassess post-intervention. The virtual group will be conducted within a secure platform such as Microsoft WebEx. Assessments (pre-, post-, mid-way) will be distributed through REDCap, a secure virtual platform, as will session handouts and forms. If participants do not have headphones, these will be provided by the study team. The biostatistician will assist with the assessment of change over time within the instrumentation. The session content for this group is built on clinical experience and empirically informed practices, drawing upon elements of Acceptance and Commitment Therapy and Meaning Making approaches. Investigators/facilitators believe that in these unique times, it is optimal to pull elements from various (manualized) approaches that contribute important elements to the group experience. In short, we are making intentional decisions within session design in which we draw heavily from empirically supported practices yet combine them in a manner that seems appropriate for the circumstances based on clinical judgment.

The intervention will be conducted by graduate-prepared mental health providers who are licensed or working under the supervision of a licensed provider. Providers will co-facilitate at all times, with two providers available to respond to group dynamics and follow up with individual members as needed.

The clinicians leading the group will adhere to professional, legal, and ethical guidelines of confidentiality established by professional organizations and state law. Legal and ethical exceptions to confidentiality include: A clear or present danger that the patient intends to harm her/himself or another, knowledge of the abuse or neglect of a minor child or incapacitated adult, or responses to a court subpoena or as otherwise required by law. All members of the group will be required to sign confidentiality forms, in which they agree not to disclose

Cancer within a Pandemic: A Telemental Health Intervention Designed to Augment Psychological Resilience amidst Dual Health Threats

Wake Forest Baptist Comprehensive Cancer Center
WFBCCC #01520

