9.0 Statistical Considerations

9.1 Analysis of Primary Objective

The primary outcome, the improvement of self-efficacy for young adult cancer survivors navigating pandemic conditions, will be assessed by comparing the change in the Cancer Behaviour Inventory-brief version (CBI-B) from baseline to Visit 8. With an n of 15, power of 80% and a 2-sided alpha of 0.05, the confidence interval around our baseline, Visit 4, Visit 8, and change scores would have a width of

Cancer within a Pandemic: A Telemental Health Intervention Designed to Augment Psychological Resilience amidst Dual Health Threats

Wake Forest Baptist Comprehensive Cancer Center
WFBCCC #01520

approximately 1.02 standard deviations. To test the change over the 8 weeks, a paired t-test (using the baseline and Visit 8 scores within the same patient) will be used; the expected difference in the CBI-B between the 2 scores would be no change (null hypothesis is mean is equal to 0). We would also calculate the difference between baseline and Visit 4 and test to see if that mean is significantly different from 0; this will help us understand that if a change occurs, does it occur earlier in the intervention or does the change happen closer to the end of the intervention.

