9.2 Analysis of Secondary Objectives

To reduce depression and anxiety levels through meaning-making, three instruments will provide information on baseline, Visit 8, and change over time. The CAS, MINI MAC, and Purpose in Life Test will all be utilized to estimate depression and anxiety levels. With an n of 15, the width of the confidence interval around the baseline, Visit 4, Visit 8, and change between baseline and Visit 4 as well as Visit 8 scores would be approximately 1.02 standard deviations; a paired t-test will be used to assess the change in the scores. As this is a pilot study, no adjustment in the p-value will be done for multiple comparisons.

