9.3 Exploratory Analyses

9.3.1 To assess the feasibility of conducting a telehealth support group for cancer survivors within a pandemic, we will measure how many subjects are still participating at the final visit (Visit 8); the proportion of subjects who are active at this visit can be calculated as n/enrollment (with the expectation of approximately 15 enrolled). When the sample size is 15, a two-sided 95% confidence interval for a single proportion will extend 25.3% from the observed proportion for an expected proportion of 50%; if the proportion is low or high, such as 10% or 90%, a two-sided 95% confidence interval will extend 15.2% from the observed proportion. These data could be used in sample size calculations to design future studies.

9.3.2 To assess YA cancer survivors' interest in participation in a telehealth support group within a pandemic, the data would be used to estimate the percentage of sessions attended for each participant and calculate the mean participation rate and standard deviation; these data could also be expressed as mean number of visits and standard deviation. These data could be used to help design future studies.

9.3.3 To enhance participants' strategies for engaging social connectivity and reduce feelings of isolation amidst simultaneous forces promoting self-isolation (i.e., cancer diagnosis and pandemic), the UCLA Loneliness Scale will be used. As this is a continuous measure, with an n of 15, the width of the confidence interval around the baseline, Visit 4, Visit 8, and change between baseline and Visit 4 as well as Visit 8 scores would be approximately 1.02 standard deviations; a paired t-test will be used to assess the change in the scores. As this is a pilot study, no adjustment in the p-value will be done for multiple comparisons.

Cancer within a Pandemic: A Telemental Health Intervention Designed to Augment Psychological Resilience amidst Dual Health Threats

Wake Forest Baptist Comprehensive Cancer Center
WFBCCC #01520

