9.3.4 To observe improvement in psychological resilience and flexibility skills in participants, the Acceptance and Action questionnaire (AAQ) will be used to estimate flexibility. As in 9.1, with an n of 15, the width of the confidence interval around the baseline, Visit 4, Visit 8, and change between baseline and Visit 4 and baseline and visit 8 scores would be approximately 1.02 standard deviations; a paired t-test will be used to assess the change in AAQ. As this is a pilot study, no adjustment in the p-value will be done for multiple comparisons.

9.3.5 To reduce feelings of helplessness and hopelessness, the MINI MAC will be used. With an n of 15, the width of the confidence interval around the baseline, Visit 4, Visit 8, and change between baseline and Visit 4 as well as Visit 8 scores would be approximately 1.02 standard deviations; a paired t-test will be used to assess the change in the scores. As this is a pilot study, no adjustment in the p-value will be done for multiple comparisons.

9.3.6 To increase distress tolerance, the Impact of Event Scale (IES) will be used to assess this measure. With an n of 15, the width of the confidence interval around the baseline, Visit 4, Visit 8, and change between baseline and Visit 4 as well as Visit scores would be approximately 1.02 standard deviations; a paired t-test will be used to assess the change in the scores. As this is a pilot study, no adjustment in the p-value will be done for multiple comparisons.

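### The power statement in 9.1 and 9.4 is attached to a confidence-interval width and gives no detectable effect; the width and the 10%/90% margin also need correcting

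*Combined protocol and SAP*

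**What the plan says.** Section 6.0 sets the size: "The study aims to initially recruit a single cohort of 15 patients". It is not derived from a power calculation.

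For continuous outcomes, section 9.1 introduces the interval width for the CBI-B scores and change scores with "With an n of 15, power of 80% and a 2-sided alpha of 0.05, the confidence interval around our baseline", and gives the width as about 1.02 SD. The primary test follows: "a paired t-test (using the baseline and Visit 8 scores within the same patient) will be used". The null hypothesis is a mean change of zero. No alternative, SD, important difference or detectable change is given. Section 9.4 repeats the statement in general form: "power of 80% and a 2-sided alpha of 0.05, the confidence interval around the estimate would have a width of approximately 1.02 standard deviations".

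Section 9.2 drops the power phrase but keeps the width and the test: "scores would be approximately 1.02 standard deviations; a paired t-test will be used to assess the change in the scores". Sections 9.3.3 to 9.3.6 do the same; 9.3.4 refers back explicitly: "As in 9.1, with an n of 15, the width of the confidence interval around the baseline".

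For the proportion still active at Visit 8, sections 9.3.1 and 9.4 give a margin of 25.3% at an expected 50% and, for low or high proportions, "such as 10% or 90%, a two-sided 95% confidence interval will extend 15.2% from the observed proportion". Neither section names the interval method.

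**The concern.** There are three faults, in order of weight.

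- **Power without an effect.** Power belongs to a test against a stated alternative. Here it is attached to the width of an interval, which is fixed by sample size, confidence level and SD. The only power figure in the plan therefore cannot be interpreted. A reader may take it to mean that the primary CBI-B test has 80% power for some modest change, possibly the half-width of about 0.51 SD.
- **The width.** Every section that gives 1.02 SD, apart from 9.4, sets it beside a paired t-test, which estimates the SD from 15 patients. The stated width is close to the value for a known SD, which is too narrow at this sample size.
- **The proportion margin.** A symmetric 15.2% around 90% or 10% runs past the ends of the scale. High retention is the result a feasibility study hopes to see, and it is where this type of interval performs worst.

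In a pilot, the stated precision is the main thing that tells a reader what the sample size can deliver.

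**Working it through.** **Inputs.** n = 15 (6.0, 9.4); two-sided alpha 0.05 and power 80% (9.1, 9.4); paired t-test against a mean change of 0 (9.1); stated width 1.02 SD (9.1 to 9.4); stated margins 25.3% and 15.2% (9.3.1, 9.4). Widths are in SDs of the quantity estimated: the score SD for a single visit, the change-score SD for a change.

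**1. Reproducing the stated figures**

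- Known-SD normal width: 2 × 1.95996 / √15 = 1.012 SD. The half-width is 0.506; rounded to 0.51 and doubled, it gives 1.02. Power does not enter.
- Wald margin at 50%: 1.96 × √(0.25/15) = 25.3%.
- Wald margin at 10% or 90%: 1.96 × √(0.09/15) = 15.2%.

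The margins reproduce exactly to the stated rounding. The 1.02 reproduces to within 1%. The documents do not show how it was obtained.

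**2. The width that matches the planned test (14 df)**

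- 2 × 2.14479 / √15 = 1.108 sample SDs. The shortfall is 1 − 1.02/1.1076 = 7.9%.
- In true SDs, the expected t width is 1.1076 × 0.9823 = 1.088, a shortfall of 1 − 1.02/1.088 = 6.2%. The factor 0.9823 is the ratio of the expected sample SD to the true SD at n = 15.
- Coverage of an interval 1.02 sample SDs wide: P(|t₁₄| < 0.51 × √15) = 93.2%.
- t widths at n = 16, 17 and 18 are 1.066, 1.028 and 0.995, so a width of at most 1.02 would need 18 patients.
- Reading the 80% as 80% assurance on the width does not rescue the sentence: that width is 1.261 SD.

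**3. Power of the planned test**

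Noncentral t, two-sided 0.05, 15 complete pairs, change in SDs of the change score:

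| Mean change | Power |
|---|---|
| 0.50 | 44% |
| 0.60 | 58% |
| 0.70 | 71% |
| 0.78 | 80% |

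The plan gives no dropout allowance. If 12 patients gave both scores (80% retention, an assumption), the t width would be 1.27 SD and the change detectable with 80% power 0.89 SD. With 10 (also an assumption), these become 1.43 SD and 1.00 SD.

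**4. The proportion**

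- Implied limits: 90% + 15.2% = 105.2%; 10% − 15.2% = −5.2%.
- Neither 10% nor 90% can be observed with 15 patients (1.5 or 13.5 patients).
- Exact binomial coverage of nominal 95% intervals at n = 15 and true retention 90%: Wald 79%, Wilson 94%, Clopper-Pearson 99%.
- At 14/15 active (93.3%): Wilson 70.2% to 98.8%, Clopper-Pearson 68.1% to 99.8%.
- If all 15 stay, the Wald interval has zero width. At true retention of 90% this happens with probability 0.9¹⁵ = 21%.

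**The case against.** The strongest reply is that little depends on these figures. This is a pilot, 15 was not derived from power, no decision rule uses the retention interval, and the final analysis would use t quantiles whatever the planning sentence says. That is true. It limits the weight of the point, but it does not make a power figure without an effect size meaningful.

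On the width, the plan says the figure is approximate, and a known-SD formula is an ordinary planning shortcut. The gap is 0.09 SD in full width, under 0.05 SD per side, and nobody plans to report an interval fixed at 1.02 SD. Even so, a shortfall of about 8% is more than rounding, and it always makes the precision look better. It is also fair to say that the origin of 1.02 is not established. A two-sample normal calculation with 15 per arm and 80% power gives a detectable difference of (1.960 + 0.842) × √(2/15) = 1.023, which fits both the 1.02 and the power phrase. But this study has one arm, so on that origin the figure would be neither an interval width nor relevant here.

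On the proportion, the arithmetic is correct, the quantity is exploratory, and the out-of-range limits are an implication rather than something the plan prints. The Wald coverage also depends on the true value: 79% at 90% retention, 81% at 80% and 95% at 70%. Taken alone, the unnamed method would be a missing detail. But the text does say that a 95% interval will extend 15.2% at those values, and at n = 15 it cannot properly do so.

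**Conclusion.** The concern holds and should be fixed. The power phrase in 9.1 and 9.4 has no meaning where it stands, and the plan omits the figure a reader needs: about 0.78 SD of the change score for 80% power, with only 44% power at 0.5 SD. The stated width is 7.9% too narrow (1.02 against 1.108 sample SDs). The 15.2% margin is a correct Wald value that is unsuitable at 10% or 90% with 15 patients.

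These figures assume 15 complete pairs and roughly normal change scores. The documents give neither the SD of the CBI-B change nor the pre-post correlation, so 0.78 SD cannot be converted to CBI-B points. Whether such a change is plausible or clinically important cannot be judged from the plan. The missing detectable effect is the most important part; the proportion margin is the least.

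**What to change.** 1. In 9.1 and 9.4, delete the reference to 80% power from the interval sentences.
2. In 9.1, 9.2, 9.3.3 to 9.3.6 and 9.4, replace 1.02 with about 1.11, or state the derivation if another quantity was meant.
3. In 9.4, state the sensitivity once, for example: *With 15 complete pairs the 95% t-based confidence interval is about 1.11 SD wide, in SDs of the quantity estimated (score or change score). The two-sided 0.05 paired t-test has 80% power for a mean change of about 0.78 SD of the change score.*
4. In 9.3.1 and 9.4, name the interval method for the retention proportion (Wilson or Clopper-Pearson) and replace the 10%/90% sentence with an attainable result, for example: *If 14 of 15 are active at Visit 8, the 95% interval is 70% to 99% (Wilson) or 68% to 99.8% (exact).*

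The cost is wording only. The stated precision becomes slightly less favourable; the sample size, tests and endpoints do not change.

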9.5 Estimated Accrual Rate

The study should accrue all subjects within a short period of time, approximately 4 weeks, based on a goal of 3 to 4 patients each week.

Appendix A – Eligibility Checklist

IRB Protocol No.	WFBCCC Protocol No. 01520
Study Title: Cancer within a Pandemic: A Telehealth Intervention Designed to Augment Psychological Resilience amidst Dual Health Threats	
Principal Investigator: [name].	

Inclusion Criteria (as outlined in study protocol)	Criteria is met	Criteria is NOT met	Source Used to Confirm * (Please document dates and lab results)
Documented cancer diagnosis within the WFBMC medical record			
Meets all pre-screen eligibility criteria			
Outpatient Cancer Survivor (diagnosis, treatment, or post-treatment)			
Aged 18-39			
Must speak English			
Must have computer with audio and visual capabilities			
Must live within North Carolina			
Must have experienced health-related anxiety and/or distress in last 3 months			
Exclusion Criteria (as outlined in study protocol)	Criteria NOT present	Criteria is present	Source Used to Confirm * (Please document dates and lab results)
Active inpatient hospitalization;			
Major cognitive impairment, marked concerns with working memory, concentration, or word finding difficulties that significantly impairs daily functioning documented in most recent clinic note or self-reported;			
Recent suicide attempt(s), psychiatric hospitalization, or psychotic processing (last 3 years);			

Cancer within a Pandemic: A Telemental Health Intervention Designed to Augment Psychological Resilience amidst Dual Health Threats

Wake Forest Baptist Comprehensive Cancer Center
WFBCCC #01520

Bipolar disorder (I or II) diagnosis, as evidenced by an ICD-10 code within the past year or revealed during subject interview			
Moderate to severe alcohol or drug abuse; as evidenced by an ICD-10 codes related to alcohol or illicit substance abuse in the medical record within the past year or revealed during subject interview.			
Severe eating disorders; as evidenced by an ICD-10 code in the medical record such as anorexia nervosa or bulimia within the past year or revealed during patient interview			
Repeated “acute” crises for example: repeated acute crises consisting of marked psychological distress that impairs function and warrants clinician intervention (e.g., occurring once a month or more frequently); this will be evaluated by the clinician screener			

This subject is eligible / ineligible for participation in this study.

OnCore Assigned PID: _____

Signature of research professional confirming eligibility: _____

Date: ____ / ____ / ____

Signature of Treating Physician: _____

Date: ____ / ____ / ____

Signature of Principal Investigator**: _____

Date: ____ / ____ / ____

* Examples of source documents include clinic note, pathology report, laboratory results, etc. When listing the source, specifically state which document in the medical record was used to assess eligibility. Also include the date on the document. Example: “Pathology report, 01/01/14” or “Clinic note, 01/01/14”

**Principal Investigator signature can be obtained following registration if needed

Cancer within a Pandemic: A Telemental Health Intervention Designed to Augment Psychological Resilience amidst Dual Health Threats

Wake Forest Baptist Comprehensive Cancer Center
WFBCCC #01520

Appendix B – Protocol Registration Form

DEMOGRAPHICS

Patient: Last Name: _____ First Name: _____

MRN: _____ DOB (mm/dd/yy): ____ / ____ / ____

ZIPCODE: _____

:

SEX: Male Female Ethnicity (choose one): Hispanic
 Non-Hispanic

Race (choose all that apply): WHITE BLACK ASIAN
 PACIFIC ISLANDER NATIVE AMERICAN

Height: _____.____ inches Weight: _____.____ lbs.(actual)

Surface Area: _____.____ m²

Primary Diagnosis: _____

Date of Diagnosis: ____ / ____ / ____

Performance Status: ____ ECOG

PROTOCOL INFORMATION

Date of Registration: _____ / _____ / _____

MD Name (last) : _____

Date protocol treatment started: _____ / _____ / _____

Informed written consent: YES NO

(consent must be signed prior to registration)

Date Consent Signed: _____ / _____ / _____

PID # (to be assigned by OnCore): _____

Protocol Registrar can be contacted by calling [contact] between 8:30 AM and 4:00 PM, Monday – Friday.

Complete the eligibility checklist in WISER and then give the completed Eligibility Checklist and Protocol Registration Form must be hand delivered, faxed or e-mailed to the registrar at [contact] or [contact], respectively.

Cancer within a Pandemic: A Telemental Health Intervention Designed to Augment Psychological Resilience amidst Dual Health Threats

Wake Forest Baptist Comprehensive Cancer Center
WFBCCC #01520

Appendix C - Race & Ethnicity Verification Form

Thank you so much for helping us to verify your race and ethnicity to ensure the quality of our information. As a brief reminder, the information you provide today will be kept confidential.

1. Are you:
 Hispanic or Latino/a
 Not Hispanic or Latino/a
2. What is your race? One or more categories may be selected.
 White or Caucasian
 Black or African American
 American Indian or Alaskan Native
 Asian
 Native Hawaiian or Other Pacific Islander
 Other, Please Specify: _____

Internal use only:

Name: _____ MRN#: _____

Was the self-reported race and ethnicity of the participant verified at the time of consent?

Yes No

Was a discrepancy found? Yes No

If yes, please provide what is currently indicated in the EMR:

Ethnicity: _____ Race: _____

Additional comments: _____

Cancer within a Pandemic: A Telemental Health Intervention Designed to Augment Psychological Resilience amidst Dual Health Threats

Wake Forest Baptist Comprehensive Cancer Center
WFBCCC #01520

Appendix D Safety and Toxicity Review Committee Serious Adverse Events SOP

Data and Safety Monitoring Committee (DSMC) Serious Adverse Event (SAE) Notification SOP	Date: 02/11/2021
---	-------------------------

Mandatory DSMC SAE Reporting Requirements in WISER

This document describes reporting requirements of adverse events from **WFBCCC Investigator Initiated interventional trials to the Data and Safety Monitoring Committee (DSMC)**. A trial is considered a **WFBCCC Investigator Initiated interventional trial** if the following criteria are met:

- 1) The Principal Investigator (PI) of the trial is a member of a department at the Wake Forest University Baptist Medical Center.
- 2) WFBCCC is considered as the primary contributor to the design, implementation and/or monitoring of the trial.
- 3) The trial is designated as “Interventional” using the Clinical Research Categories definitions provided by the NCI in the Data Table 4 documentation.
(<https://cancercenters.cancer.gov/GrantsFunding/DataGuide#dt4>)

There are two distinct types of WFBCCC Investigator Initiated interventional trials based on where patient enrollment occurs. These include:

- 1) Local WFBCCC Investigator Initiated interventional trials defined as trials where **all patients are enrolled from one of the WFBCCC sites**. These include the main outpatient Cancer Center clinics (located in Winston-Salem) as well as WFBCCC affiliate sites located in Bermuda Run (Davie Medical Center), Clemmons, Lexington, High Point, or Wilkesboro.
- 2) Multi-Center WFBCCC Investigator Initiated interventional trials defined as trials where patients are enrolled from other sites in addition to WFBCCC sites.

There are three types of trials that are included in this category:

- a. Trials sponsored by the NCI Community Oncology Research Program (NCORP) that are conducted at multiple sites where the PI is a member of a department at the Wake Forest University Baptist Medical Center.
- b. Trials sponsored by Industry that are conducted at multiple sites and the PI is a member of a department at the Wake Forest University Baptist Medical Center.
- c. Trials sponsored by WFBCCC that are conducted at multiple sites and the PI is a member of a department at the Wake Forest University Baptist Medical Center.

All Adverse Events (AEs) and Serious Adverse Events (SAEs) that occur on any patients enrolled on WFBCCC Investigator Initiated Interventional trials must be entered into the WISER system. The only exception to this requirement is for patients enrolled on NCORP trials at non- WFBCCC sites. AEs and SAEs for NCORP patients enrolled at WFBCCC sites must be entered into the WISER system. Once these

Cancer within a Pandemic: A Telemental Health Intervention Designed to Augment Psychological Resilience amidst Dual Health Threats

Wake Forest Baptist Comprehensive Cancer Center
WFBCCC #01520

AEs and SAEs are entered in WISER, certain actions must be taken regarding the reporting of specific Adverse Events to the DSMC.

All Adverse Events that occur during protocol intervention (defined below) and are coded as either 1) **unexpected grade 4**, 2) **unplanned inpatient hospitalization > 24 hours (regardless of grade)**, or **grade 5 (death)** must be reported to the DSMC using the SAE console in WISER.

A research nurse or clinical research coordinator when made aware that an adverse event meets one of the above criteria has occurred on a WFBCCC Investigator Initiated interventional trial, is responsible for informing a clinical member of the DSMC by phone (or in-person) about the adverse event. The nurse/coordinator should contact the treating physician prior to calling the DSMC clinical member to obtain all details of the SAE, as well as all associated toxicities to be recorded along with the SAE. In addition, this nurse or coordinator is responsible for entering the adverse event information into the SAE console in WISER. Once the adverse event has been entered into the SAE console an email informing the entire DSMC will be generated.

THESE REPORTING REQUIREMENTS APPLY TO any staff member on the study team for a WFBCCC Institutional Interventional trial. Ultimately, the protocol PI has the primary responsibility for AE identification, documentation, grading and assignment of attribution to the investigational agent/intervention. However, when an AE event as described above is observed, it is the responsibility of the person who observed the event to be sure that it is reported to the DSMC.

What is considered during protocol intervention?

During protocol intervention is considered to be the time period while a patient is on study treatment or during the time period within 30 days of last study treatment (even if patient begins a new (non-study) treatment during the 30 days). This window of 30 days should be the standard window to be used in all protocols unless a specific scientific rationale is presented to suggest that a shorter window can be used to identify events. If it is a trial sponsored by Industry and the sponsor requires a longer window for monitoring of SAEs, then the longer window of time specified by the sponsor should be followed.

What is considered as an Unexpected Grade 4 event?

Any grade 4 event that was not specifically listed as an expected adverse event in the protocol should be considered as unexpected. A grade 4 adverse event can be considered to be unexpected if it is an event that would not be expected based on the treatment being received or if it is unexpected based on the health of the patient. In either case, if there is any uncertainty about whether a grade 4 adverse event is expected or unexpected it should be reported to DSMC.

DSMC notification responsibilities of the person (e.g., nurse) handling the reporting/documenting of the SAE in WISER:

1. Make a phone call (or speak in person) to the appropriate clinical member of the DSMC according to the schedule as listed below (page if necessary).

Cancer within a Pandemic: A Telemental Health Intervention Designed to Augment Psychological Resilience amidst Dual Health Threats

Wake Forest Baptist Comprehensive Cancer Center
WFBCCC #01520

2. Enter a new SAE into the SAE module that is located in the Subject>> CRA Console in WISER WITHIN 24 HOURS of first knowledge of the event. Information can be entered and saved, but the DSMC members will not be notified until a date is entered into the DSMC Notification Date Field. This will ensure that all persons that need to be made aware of the event (i.e., PI, study team members and DSMC members) will be notified; remember to file a copy of the confirmation.
3. Document that the appropriate person(s) on the DSMC has been contacted. Indicate the name of the DSMC clinician that was contacted and the date and time contacted in the Event Narrative field in the SAE console of the particular subject.
4. Document whether or not the protocol should be suspended based on the discussion with the DSMC clinician. This is the major function of the email notification. Enter whether the protocol should be suspended in the Event Narrative Field.
5. Follow up/update the clinical member(s) of DSMC regarding any new developments or information obtained during the course of the SAE investigation and reporting process.

Elements needed to complete the SAE form in the Subject Console in WISER (see Screen Shot 3):

1. Event Date
2. Reported Date
3. Reported by
4. If Grade 5, enter Death Date
5. If Grade 5, enter Death occurred: within 30 days
6. Event Narrative: Brief description (include brief clinical history relevant to this event, including therapies believed related to event). Begin narrative with the DSMC clinician who was notified and Date/Time notified. In addition, state attribution by DSMC clinician as either “Unrelated”, “Unlikely”, “Possibly”, “Probably”, or “Definitely”. Always include the following here:
 - i. DSMC clinician name, date/time contacted and comments
 - ii. Date of last dose before the event
 - iii. Is suspension of the protocol needed? Y/N
7. Treating Physician comments
8. PI comments, if available
9. Protocol Attribution after discussion with DSMC clinician
10. Outcome (Fatal/Died, Intervention for AE Continues, Migrated AE, Not Recovered/Not Resolved, Recovered/Resolved with Sequelae, Recovered/Resolved without Sequelae, Recovering and Resolving)
11. Consent form Change Required? Y/N
12. SAE Classification ***This is required in order for the email notification to be sent***
13. Adverse Event Details – Enter all details for each AE associated with the SAE.
 - a. Course start date
 - b. Category
 - c. AE Detail
 - d. Comments
 - e. Grade/Severity
 - f. Unexpected Y/N

Cancer within a Pandemic: A Telemental Health Intervention Designed to Augment Psychological Resilience amidst Dual Health Threats

Wake Forest Baptist Comprehensive Cancer Center
WFBCCC #01520

[figure not shown]
- g. DLT Y/N
- h. Attributions
- i. Action
- j. Therapy
- k. Click ADD to attach the AE Detail to the SAE.

14. Enter Date Notified DSMC -- ***This is required for the email notification to be sent***

